#### 10.4.2 ANALYSIS OF THE PRIMARY EFFICACY ENDPOINT(S)

Primary and secondary endpoints are operationalized above (i.e., mean within-person differences between placebo and experimental in final seven days of manipulation) for the daily SITB suicidal ideation and planning subscales (primary endpoints) as well as the daily UPPS-P impulsivity, PROMIS anxiety, CESD depression, BHI hopelessness, and SSES rejection sensitivity subscales (secondary endpoints).

**Analyses will proceed identically for all outcomes listed above.** First, we will calculate each subject's mean daily rating (via phone) on the outcome measure *in the final seven days of both the placebo condition* (placebo mean score) and the experimental condition (experimental mean score).

Second, we will utilize paired samples t-tests to examine the within-person condition effect. If proposed covariates (medicines, BMI, age) show sufficient variability, we will instead use a repeated measures ANCOVA to evaluate the condition effect. These analyses will be conducted on the intent-to-treat dataset.

If necessary due to violations of model assumptions, we will utilize similar nonparametric tests.

---

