### Randomized Subject to a *Condition Order*

**Condition Order 1:** Placebo during visits 1-3, Experimental during visits 4-6 (n=15)

**Condition Order 2:** Experimental during visits 1-3, Placebo during visits 4-6 (n=15)

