### 5 STUDY ENROLLMENT AND WITHDRAWAL

#### 5.1 PARTICIPANT INCLUSION CRITERIA

In order to be eligible to participate in this study, an individual must meet all of the following general criteria:

- Provision of signed and dated informed consent form
- Stated willingness to comply with all study procedures and availability for the duration of the study
- Ability to take oral medication and be willing to adhere to the medication regimen

To be eligible for participation, an individual must also meet all of these study-specific following criteria.

1. Must be biologically **female** and between the ages of **18-45 years**.
  - **Justification:** Women younger than 18 or older than 45 may have inconsistent menstrual cycles or may be postmenopausal and therefore no longer cycling.
2. Must have **normal menstrual cycles** between 25 and 35 days.
  - **Justification:** Abnormal menstrual cycle lengths or variability in lengths could introduce error variance into the experiment, and could reduce confidence regarding the timing of the experimental manipulation to cycle events.
3. Must be under the **current care** of an outpatient mental health provider.
  - **Justification:** Because we intend to recruit women with current suicidality, engagement with a mental health provider is required as a protective measure to ensure that participants have access to treatment if needed.
4. If the woman has children, she must be at least **1 year postpartum**.
  - **Justification:** The postpartum period can be characterized by altered hormone levels and changes; therefore, postpartum women may introduce error variance into the experiment.
5. Must be of **normal weight** (BMI between 18-29 kg/m^2); measured at the enrollment visit.
  - **Justification:** Responses to doses of hormones may vary by BMI and risk for thromboembolic events with hormone use increases in obese women.
6. Must report **at least some recent suicidal ideation (in the past month)** at enrollment.

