## 10 STATISTICAL CONSIDERATIONS

### 10.1 STATISTICAL AND ANALYTICAL PLANS

There will be no formal SAP. The PI will conduct all analyses at the end of the trial.

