### 10.4 DESCRIPTION OF STATISTICAL METHODS

#### 10.4.1 GENERAL APPROACH

The design of this study is a two-period crossover design, where each of two study periods is a perimenstrual frame of the menstrual cycle (days +7 to +22 following ovulation where positive ovulation test day=0). Each participant will complete both conditions in a randomized order.

The primary windows of comparison will be the final seven days of each administration phase, which will allow for a comparison of a woman's mean scores in the placebo condition compared to her mean scores in the experimental condition.

Primary hypothesis tests will be evaluated using a alpha level of .05, with a two-tailed test.

All outcomes will be checked for normality; given the low likelihood that suicidality will follow a normal distribution even in this clinical sample, we expect that we will need to utilize nonparametric procedures.

---

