### 10.5 SAMPLE SIZE

An unlimited number of women will be screened. 45 women will be enrolled in the study, with the goal of 30 women completing the study.

Power analyses are described below; alpha is set at .05, power at 80%. The null hypothesis is no link between the study experimental condition and risk for suicidal ideation, intent, and planning; the alternate hypothesis is that hormone stabilization in the experimental condition will prevent flux in these suicide-related outcomes. Because no previous studies have examined the impact of experimental hormones on suicidality, we have conducted power analyses using existing effect sizes on related constructs (e.g., BPD features).

**Power Analysis.** For the contrast testing the primary hypothesis, we will have power to detect a conventionally medium-sized effect of hormone withdrawal ( $r = .30$ ;  $d = .60$ ) at 80% power with just 17 participants. The PI's previous work in women with BPD suggests that attrition could be as high as 25% across two conditions; should attrition be this high, enrollment of 22 participants would be required for adequate power. However, to improve generalizability of our findings and to ensure 80% power to detect small-to-medium effect sizes ( $r = .20$ ;  $d = .40$ ), we aim to include 30 completers (with 45 women randomized). This number is especially reasonable given the

much larger effects found in the candidate's recent studies for the effect of natural ovarian steroid changes (average  $r = .58$ ;  $d = 1.38$ ) on daily symptoms of depression, rejection sensitivity, anxiety, and impulsivity.

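### The primary test for this two-period crossover has no period or order term: if scores shift between cycles, power is lost, and unequal completion adds bias. Period should be modelled on observed, not carried-forward, scores.

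*Combined protocol and SAP*

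**What the plan says.** Section 10.4.1 states: "The design of this study is a two-period crossover design", with each woman completing both conditions in random order. Section 10.4.2 averages each woman's daily phone ratings over the final seven days of each condition and continues: "Second, we will utilize paired samples t-tests to examine the within-person condition effect". If medicines, BMI and age vary enough, a repeated measures ANCOVA replaces the t-test. The same analysis serves both primary and all five secondary endpoints.

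On distribution, Section 10.4.1 says "we expect that we will need to utilize nonparametric procedures", and Section 10.4.2 says only "we will utilize similar nonparametric tests". No rank test is named.

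Section 10.3 prescribes an intent-to-treat dataset with carry-forward. Section 10.1 says "There will be no formal SAP", so no later document is planned to add model terms. Section 10.5 says "45 women will be enrolled in the study, with the goal of 30 women completing the study", and the schematic shows 15 women per order.

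**The concern.** In a two-period crossover, any general change between periods adds to the placebo-minus-active difference in one order and subtracts from it in the other. A test that pools the differences around one mean treats that change as noise. If the two orders contribute unequal numbers, part of the change also enters the estimate.

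A change is possible here. Women enter on past-month ideation, stay in usual care and take part for about 3.5 months (Protocol Summary, Sections 4.1 and 5.1). Section 4.1 says the scoring of the lab tasks controls for experience-related change; nothing comparable is stated for the daily phone endpoints. At stake is a missed hormone effect or, with unequal completion, a cycle-to-cycle change reported as a hormone effect in either direction.

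**Working it through.** **The plan's own figures.** Section 10.5 claims 80% power (alpha .05; two-tailed in Section 10.4.1) with 17 women at d = .60 and gives 30 completers for d = .40. If d is the mean difference divided by the SD of the paired difference (d_z), a two-sided paired t-test has 64% power at 17 and 56% at 30. The stated 80% is therefore not reproduced on that reading. Section 10.5 does not say how d is standardised, so d_z of .40, .53 and .60 are carried below as assumptions. At 30 completers, .53 is the value that gives 80%.

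**Set-up.** Let D be a woman's placebo mean minus her active mean, with SD 1 within each order. Let δ be the condition effect and π the excess of period 1 over period 2 in the same SD units. D has mean δ + π in the placebo-first order (n1 women) and δ − π in the active-first order (n2 women), with n = n1 + n2.

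- Paired estimate: δ + π(n1 − n2)/n.
- Order-adjusted estimate, the equally weighted average of the two order means: δ, whatever n1 and n2 are. Its standard error is ½√(1/n1 + 1/n2), with n − 2 df.
- Variance used by the paired test at equal orders: about 1 + π²n/(n − 1). At π = .5 and n = 30 this is 1 + .25 × 30/29 = 1.259. The test therefore uses a standard error of about √(1.259/30) = .205 when the true one is √(1/30) = .183.

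**Equal completers, 15/15** (simulated, normal differences):

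| d_z | Paired t, π = 0 / .25 / .5 / .75 | Order-adjusted, any π |
|---|---|---|
| .40 | 56 / 54 / 47 / 36% | 56% |
| .53 | 80 / 79 / 73 / 63% | 80% |
| .60 | 89 / 87 / 83 / 76% | 89% |
| 0 (type I error) | 5 / 4.4 / 2.8 / 1.5% | 5% |

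The rank tests behave alike. At d_z .40 and π = .25/.5/.75, signed-rank has 53/45/34% power, against 52–53% for a rank-sum test of period differences between orders.

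**Unequal completers, π = .5, women with both periods.**
- 18/12: bias .5 × 6/30 = .10 SD and type I error about 5%. At d_z .40, power is 68% or 28% depending on the direction of the shift, against 54% adjusted.
- 20/10: bias .5 × 10/30 = .17 SD and type I error about 10%, against 5% adjusted.

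**How likely is that imbalance?** Suppose 45 women are randomised 23/22 and 15 drop out at random. The root-mean-square of n1 − n2 is then 3.27, so RMS bias is π × 3.27/30 = .027/.054/.082 SD for π = .25/.5/.75. A split of 18/12 or worse has probability 12%, and 20/10 or worse .5%. At d_z .40, power averaged over such dropout is 55/49/41%, against 55–56% adjusted. At π = .5 the paired test rejects a true null 3.6% of the time.

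**Carried-forward data.** Section 10.3 does not say what is carried. Assume period 1 scores are copied into period 2, so that 15 of 45 women have a difference of zero. With π = .5 and no condition effect:

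| Completers | Bias, paired | Bias, order-adjusted | Type I error, paired → adjusted |
|---|---|---|---|
| 18/12 | .5 × 6/45 = .067 | ½(.5 × 18/23 − .5 × 12/22) = .059 | 5.2% → 6.5% |
| 20/10 | .5 × 10/45 = .111 | ½(.5 × 20/23 − .5 × 10/22) = .104 | 10.2% → 12.5% |

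The zeros dilute the two order groups unequally, so the shift no longer cancels, while the order term still shrinks the error variance.

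**The case against.** **No shift is documented.** This stands, and the point is conditional on one. Some text argues against a large shift: period 1 starts only seven days after a later positive ovulation test (Section 7.3.3), so some settling may come first, and Section 5.1 describes habitual ideation. At .25 SD with equal orders the loss is one to three points.

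**Other sections might fill the gap.** They do not. Section 10.4.6 says the primary models control for baseline differences, but a change between cycles is not one. Section 6.1.9 mentions multilevel models without giving terms. Section 10.2 frames the hypothesis as a Lab 2 minus Lab 1 change within each condition, which would cancel an additive shift between cycles, but Section 10.4.2 does not use that contrast for the endpoints.

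**The order term does not rescue the planned dataset.** This is the strongest objection, and it stands. A reader might infer that adding order to the existing plan removes both the power loss and the bias. With carry-forward and unequal completers it leaves about nine tenths of the bias and makes false positives more frequent. Its power gain at d_z .40 also falls to about 0/3/8 points at shifts of .25/.5/.75. The period term therefore has to come with observed data.

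**The figures assume normal differences.** Section 10.4.1 itself doubts normality, so the power figures are indicative. The unnamed rank test is a specification gap rather than evidence of error: the natural reading of a similar test is signed-rank, which also ignores period.

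**Conclusion.** The omission is real and worth correcting as a low-cost, conditional improvement. With equal completers and no carry-forward, the paired test stays unbiased and, if there is a shift, becomes conservative. At d_z .40 the loss is about 2, 9 and 20 points of power for assumed shifts of .25, .5 and .75 SD; with no shift nothing is lost.

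Two stronger readings are not supported. One is that the planned test inflates type I error or is materially biased as designed. Averaged over random dropout, the paired test stays below 5% at a .5 SD shift. Clear inflation needs an imbalance of about 20/10, which in practice means dropout related to order, and the documents give no evidence of that. The other is that the correction restores the 80% power in Section 10.5. At d_z .40 the adjusted test still has about 56%, which is a separate sample-size matter.

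**What to change.** In Section 10.4.2, estimate the condition effect with period in the model, from observed period data without carry-forward. Either of these serves:

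- a mixed model with condition, period and a random effect for woman; or
- among women with both periods, a regression of the placebo-minus-active difference on order, taking the equally weighted average of the two order groups as the condition effect (n − 2 df).

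Add period to the ANCOVA if it is used. Name the rank version as a rank-sum test comparing period 1 minus period 2 differences between the two orders. Do not apply the order term to Section 10.3's carried-forward scores; if a carry-forward analysis is kept, make it a sensitivity analysis, and amend Section 10.3 to match.

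The cost is one degree of freedom and a few sentences; order is already recorded. With no shift, power at d_z .40 goes from 56.3% to 56.2% at 15/15, 54.5% at 18/12 and 51.4% at 20/10. Rank-sum costs about 2 points against signed-rank at 15/15 (54.5% to 52.1%).

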**Assessment of Outcomes.** Participants will complete phone measures of symptoms and suicidality starting on the first day of patches/pills and ending 5 days following the last patch/pill (phone symbols in figure above). Three lab sessions will measure mediating constructs using behavioral tasks. In each condition, lab visits will occur on days +7, +14, and +22 following ovulation.

**Primary Windows of Comparison for Hypothesis Testing.** To test whether prevention of E2/P4 withdrawal is associated with mediating behavioral constructs and suicide risk, we will compare tasks and interviews in **LABPL2** with **LABEXP2**.

**Blinding of Participants and Staff.** All study staff performing assessments will remain blinded to condition. The natural within-woman variation in menstrual cycle length from one cycle to another will help maintain the participant blind. Few women have regular 28 day cycles, and between-cycle variation up to 8 days is normal. Demand characteristics regarding the impact of hormonal manipulation will be minimized by informing participants that women vary a great deal in their responses to hormones, and our current evidence does not allow us to predict for certain whether hormones have a positive, negative, or neutral effect on women's symptoms (of note, this is scientifically accurate). Finally, although some women may become unblinded later in the extended hormone phase, work by the mentoring team suggests that pharmacologic delay of menses does not influence the course of perimenstrual mood symptoms.

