**Follow-Up Timeline:**

**Condition 1 (Follow-Up Visits 1-3):**

- Negative Pregnancy Test Confirmed at Enrollment
- Ovulation Testing
- Positive Ovulation Test #1= Day 0
- Study Followup Visits 1-3 Scheduled for days +7, +14, +22
- Study Followup Visit 1 (Day +7): Assessments, administration of study agent patch A and dispensation of pills (**Condition 1**)
- Study Followup Visit 2 (Day +14): Assessments, replacement of study agent patch A with patch B (**Condition 1**)
- Removal of study patch and end of pills on day +21
- Study Followup Visit 3 (Day +22): Assessments, Pregnancy Test

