### 10.2 STATISTICAL HYPOTHESES

**Hypotheses.** For suicidal desire and suicidal action capacity—our primary endpoints (see far right side of figure in Figure at right)—we predict that perimenstrual increases in suicidal desire and action capacity (Lab 2 – Lab 1 within each condition) will be larger in the placebo condition than in the experimental hormone stabilization condition. The associated null hypothesis is that there will be no difference in the perimenstrual increase in suicidality across condition. For our secondary endpoints, including hopelessness, negative social appraisals, reduced inhibitory control, and threat sensitivity, we predict the same pattern of results.

[figure not shown]

Figure 1. Pathophysiological Model of Increased Perimenstrual Suicide Risk

There are no “efficacy” endpoints in the present trial since it is mechanistic and not a treatment study.

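### The primary comparison leaves the day +7 score unused; adding it as a covariate is a cheap gain in precision of unknown size, not the repair of an error

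*Combined protocol and SAP*

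**What the plan says.** Section 10.4.2 computes each woman's mean daily phone rating over the last seven days of each condition, and "we will utilize paired samples t-tests to examine the within-person condition effect". A repeated measures ANCOVA replaces the t-test if medicines, BMI or age vary enough. Nonparametric tests follow if assumptions fail, which 10.4.1 expects for suicidality. Section 10.4.1 adds: "Primary hypothesis tests will be evaluated using a alpha level of .05, with a two-tailed test".

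A start-of-condition score exists twice over. In section 4.1, "Participants will complete phone measures of symptoms and suicidality starting on the first day of patches/pills". In the section 7.3.3 timeline, condition 1 opens with "Study Followup Visit 1 (Day +7): Assessments, administration of study agent patch A and dispensation of pills", and visit 4 is described the same way for condition 2.

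Two other sections refer to a baseline. Section 10.2 predicts that the increase from Lab 1 to Lab 2 "will be larger in the placebo condition than in the experimental hormone stabilization condition". Section 10.4.6, on comparing the two order groups, dispenses with inferential tests because the primary modelling is said to control for baseline differences. The model in 10.4.2 contains no baseline term.

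**The concern.** Pairing removes what is stable about a woman. It does not remove what is particular to a cycle: a bad month raises both the day +7 score and the final-week mean, whatever she is taking. The difference between her two day +7 scores carries information on that noise. Age and BMI barely change between two nearby cycles, so as main effects they cannot sharpen her own condition difference.

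The trial aims for only 30 completers and names d = .40 as the effect it wants to detect. Unused information matters more at that size. There is also no formal SAP (section 10.1), so a covariate not named now could not credibly be chosen after unblinding.

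**Working it through.** **The plan's own figures.** Section 10.5 claims "we will have power to detect a conventionally medium-sized effect of hormone withdrawal" (d = .60) "at 80% power with just 17 participants", and 80% power at d = .40 with 30 completers. Take d as the mean within-woman difference divided by its SD, with a two-sided .05 test.
- d = .60: ((1.960 + 0.842)/.60)² = 21.8, so 22 women, or 24 with the t distribution. Power at 17 is 64%.
- d = .40: ((1.960 + 0.842)/.40)² = 49.1, so 50 women, or 52 with the t distribution. Power at 30 is 56%.

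Neither stated figure is reproduced. If d is instead in units of the SD of a single score, they need unstated between-condition correlations of about .66 and .72. That is a separate matter. The comparison below does not depend on it.

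**Model.** Let D be a woman's placebo-minus-stabilization difference in final-week means, and B her day +7 difference. Regress D on B and on order coded -1/2, +1/2, with 15 women per order as in the schematic. Test the intercept.

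- Without B: variance factor 1, df 28, noncentrality .40 × √30 = 2.19, power .56. The plain paired t-test (df 29) also gives .56.
- With B: variance factor (1 - ρ²)(1 + 1/(n - 4)), df 27, noncentrality .40 × √(30/factor). At ρ = .5 the factor is .75 × 1.0385 = .78 and the noncentrality is 2.48.

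ρ is the correlation between B and D. The documents do not give it, so the range is an assumption.

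| ρ | Variance factor | Power |
|---|---|---|
| 0 | 1.04 | .545 |
| .2 | 1.00 | .56 |
| .3 | .945 | .58 |
| .5 | .78 | .67 |
| .7 | .53 | .83 |

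Break-even: (1 - ρ²)(27/26) = 1 gives ρ = √(1/27) = .19. In simulation without the order term, power agrees and type I error stays near 5%.

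**What ρ might be.** Suppose a one-day baseline, a seven-day-mean outcome, independent daily noise, and a share c of within-woman daily variance that belongs to the cycle. Then ρ = c/√(c + (1 - c)/7). This gives .19 at c = .09, .36 at c = .20, .47 at c = .30 and .66 at c = .50. It is an illustration only. A lab score on a different form could correlate more or less.

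**Covariate, not change score.** With equal variances, D - B has variance 2 - 2ρ times that of D, so subtraction loses whenever ρ < .5. At ρ = .3, simulated power is .44 for the change score against .56 for the paired test.

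**Order coding.** Take a true effect of .40 and a period effect of .5. With order coded 0/1 the intercept is one order's mean, for example .40 - .50 = -.10. Centred coding returns .40.

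**Missing baselines.** Section 5.3 reports 85% completion of daily surveys in an earlier study and expects better here. If 85% applied to one particular call in each condition, with independent misses, .85² = .72 of women would have both, about 22 of 30. Complete-case power would be .44 at ρ = .3 and .52 at ρ = .5, below the unadjusted .56. Setting a missing B to zero keeps all 30 women. In simulation with 28% missing, power is about .55, .58, .63 and .73 at ρ = 0, .3, .5 and .7, with type I error near 5%.

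**The case against.** The paired t-test is a legitimate analysis of the endpoint in section 4.2.1. A reader might infer that omitting the baseline biases or invalidates it. The documents do not support that: order is randomized and each woman is her own control.

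Several practical objections stand and shape the fix.
- The first-day phone rating is not shown to be pre-dose. Section 4.1 gives only the day, and section 2.2 says oral progesterone peaks within 3 hours, so a late call could already reflect treatment. The visit 1 and visit 4 assessments are listed ahead of patch A. They use the full SITBI and the STAI, not the shortened SITBI and PROMIS of the calls, but a covariate need not share the outcome's form.
- Dropping women without a baseline could cost more than the adjustment gains, as shown above.
- Adjustment needs no carryover by day +7 of period 2. The paired test needs none only by the final week.
- The gain may be slight for planning scores, because recent concrete planning is exclusionary (section 5.1) and scores may sit near the floor.

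A reader might also suppose that a mixed model with condition, period and period-specific baseline gives the same answer. In general it does not: with random subject effects a single baseline slope blends between-woman and within-woman associations.

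Nor does the covariate turn 10.4.2 into the contrast in 10.2. Lab 2 minus Lab 1 remains a different measure and window. The sentence in 10.4.6 concerns the order groups and does not commit the plan to this covariate.

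**Conclusion.** The point holds as a recommended improvement in precision. A score already collected in both conditions is left out of the primary model, and using it has a small, bounded cost: at n = 30 and d = .40, at worst a fall from .56 to about .55. The gain is likely but of unknown size: about 2 points at ρ = .3, 11 at ρ = .5 and 27 at ρ = .7.

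It would be tempting to say that adjustment restores the intended 80% power. Within the range examined that happens only near ρ = .7, and nothing in the documents supports so high a value.

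The figures assume 30 completers balanced over order, roughly normal differences, a baseline taken before the first dose, and no carryover by day +7 of period 2.

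**What to change.** In section 10.4.2:
- Regress each woman's final-seven-day difference (placebo minus stabilization) on her day +7 difference for the matching construct and on condition order coded -1/2, +1/2. Take the intercept, at zero baseline difference, as the condition effect.
- Use the visit 1 and visit 4 lab scores as the baseline, and state that they are obtained before the first patch and pill. Use the first-day phone rating only if the plan states that it precedes the first dose.
- Keep women with a missing baseline difference by setting it to a constant, such as zero.
- Name a permutation or rank version of the same model for use if normality fails.
- Report the unadjusted paired comparison as supportive.

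Reconcile 10.2 and 10.4.6 with this text, so that the plan says in one place which baseline is used and how.

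The cost is a few lines of text, one degree of freedom and the slightly stronger carryover assumption. No new data are needed.

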**4 STUDY DESIGN AND ENDPOINTS**

**4.1 DESCRIPTION OF THE STUDY DESIGN**

[figure not shown]
This is a single-center study; there is no phase designation because it is a mechanistic experiment with agents (E2,P4) that is commonly used in clinical practice.

**Participants:** 30 female outpatients with recent suicidal ideation but **low imminent risk for suicide attempt** (see **Human Subjects** section for details) receiving treatment as usual from a mental health provider at UNC will be recruited. Women must: be 18 to 45 years of age, have normal menstrual cycles (25-35 days), not pregnant (verified with urine screens), breastfeeding, or trying to get pregnant, not taking hormones, no history of serious medical illness, normal weight (BMI 18-28 kg/m^2), and low risk for thrombotic events (factor V Leiden mutation based on family history). Use of psychotropic medications are expected in the majority of participants. *Most outpatients with suicidality take psychotropic medications; therefore, to increase feasibility and generalizability, medication use will be carefully measured daily and covaried in analyses if common enough.*

**Psychiatric Diagnoses.** Women will undergo initial SCID-I and SCID-II interviews. *History of manic episode, psychosis (except dissociation), or substance abuse disorder will be exclusionary due to increased risk of suicidal crises.* Additionally, a self-report history of treatment for postpartum depression or a current diagnosis of premenstrual dysphoric disorder will be exclusionary, since these reproductive mood disorders could be characterized by a different pathophysiological pattern of sensitivity to ovarian steroid flux. On the basis of work by [name], we expect that 50 - 75% of our sample will meet criteria for major or persistent depressive disorder, ≥ 50% will meet criteria for BPD, and ≥ 25% will meet criteria for an anxiety disorder.

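### An undefined trigger replaces the paired test with an ANCOVA whose covariate terms and condition test are not specified; one form that the text permits would take power from about .56 to about .06

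*Combined protocol and SAP*

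**What the plan says.** Section 10.4.2 averages each woman's daily ratings over the last seven days of each condition and compares the two means: "Second, we will utilize paired samples t-tests to examine the within-person condition effect". The next sentence makes that choice conditional: "If proposed covariates (medicines, BMI, age) show sufficient variability, we will instead use a repeated measures ANCOVA to evaluate the condition effect". The same steps apply to both primary and all five secondary outcomes. Section 4.1 has a second trigger, for medicines: "medication use will be carefully measured daily and covaried in analyses if common enough".

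Section 10.4.1 sets the error rate: "Primary hypothesis tests will be evaluated using a alpha level of .05, with a two-tailed test". Sections 10.4.1 and 10.4.2 also allow nonparametric tests, and 10.4.1 expects to need them for suicidality. Section 10.4.6 says that the primary models will control for baseline differences. Section 10.1 says that there will be no formal SAP, so no later document is due to settle the model.

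On the covariates, section 5.1 admits women aged 18 to 45 with BMI 18 to 29 measured at enrollment (section 4.1 gives 18 to 28). The schedule of events in 7.3.7 lists height and weight at enrollment only, while the table in 7.3.3 also lists weight at follow-up. Medicines are recorded daily.

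**The concern.** The endpoint is a difference within one woman. Age hardly moves over about 3.5 months, and BMI as measured at enrollment is a single value, so neither can explain why her two condition means differ. Such covariates can affect the condition test only through condition-by-covariate terms or through the residual variance of the difference. What they do there depends on details that the plan omits: whether interactions are fitted, whether covariates are centred, and which line of output is the primary test.

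Two things are at stake. In one form that the text leaves open, the primary test becomes an extrapolation to age 0 and BMI 0 with almost no power, and the result could be reported as no hormone effect. And because neither trigger has a threshold, the primary model for seven outcomes is chosen after the data are in.

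**Working it through.** **Inputs from the plan.** Two-sided alpha .05 (10.4.1). Section 10.5 states "alpha is set at .05, power at 80" per cent. It claims that d = .60 is detectable "at 80% power with just 17 participants", and for d = .40 says "we aim to include 30 completers (with 45 women randomized".

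**Assumptions.** The plan gives no mean or SD for age or BMI. Base case: age uniform on 18 to 45 (mean 31.5, SD 27/√12 = 7.79) and BMI uniform on 18 to 29 (mean 23.5, SD 11/√12 = 3.18), uncorrelated. Alternatives: age mean 28 to 30 with SD 6 to 8; BMI mean 23 to 23.5 with SD 2.5; age-BMI correlation 0 or .3. The scale of d is not stated. The base case takes it in SDs of the within-person difference.

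**1. The plan's own figures.** Noncentral-t power for the paired test is .64 at d = .60, n = 17 (24 women needed for 80%) and .56 at d = .40, n = 30 (52 needed). The stated 80% is not reproduced on this scale. If d is in raw-score SDs, dz = d/√(2(1−ρ)). With ρ = .7 the required numbers are 16 and 32, close to those stated, but the plan gives no ρ. The comparison below is therefore shown for both cases.

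**2. Additive age and BMI.** Terms that are constant within a woman cancel from her difference. In one simulated data set the condition estimate was −0.350, SE 0.190, t = −1.85, with or without them.

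**3. Mean-centred interactions.** Regress the difference D on centred age and BMI and test the intercept. If the covariates do not moderate the effect, its variance stays s²/n, on n − 3 = 27 df. Power is .561 at d = .40 (paired .563) and .886 at d = .60 (paired .888).

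**4. Uncentred interactions.** The intercept is now the effect at age 0 and BMI 0. Its variance is multiplied by 1 + [n/(n−1)]·m′S⁻¹m, where m holds the covariate means and S their covariance matrix:

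- age: (31.5/7.79)² = 16.33; BMI: (23.5/3.18)² = 54.77; sum 71.10
- factor: 1 + (30/29)(71.10) = 74.6; SE multiplier √74.6 = 8.6
- age alone: 1 + (30/29)(16.33) = 17.9; SE multiplier 4.2

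| n = 30, two-sided .05 | d = .40 | d = .60 |
|---|---|---|
| Paired test | .563 | .888 |
| Centred age and BMI | .561 | .886 |
| Uncentred age only | .08 | .12 |
| Uncentred age and BMI | .057 | .066 |

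Simulation with 5,000 trials at d = .40 gave .571 paired, .571 centred and .059 uncentred. Across the assumed distributions the SE multiplier is 7.8 to 10.5 and power .055 to .058. With raw-score d and ρ = .7, the paired, centred and uncentred powers are .78, .78 and .06. In the data set of step 2, the uncentred condition line became +2.24 (SE 1.68, t = 1.33), opposite in sign.

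**5. If age does moderate the effect.** With a correlation of .3 or .5 between age and D, centred adjustment raises power at d = .40 from .57 to .60 and from .56 to .66. That gain is for the effect at the sample's own covariate means. When the population mean effect is zero, the same centred test rejects .061 and .087 of the time.

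**6. Adjusting for order.** With equal orders this takes one df (29 to 28), and power at d = .40 goes from .563 to .562. If a period effect shifts D by +.5 SD in one order and −.5 SD in the other (assumed), the SD of D in the plain paired test grows to about √(1 + .25) = 1.12. Simulated power is then about .47 to .48 unadjusted and .56 to .57 adjusted.

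**The case against.** The strongest reply is that the plan names an ANCOVA and nothing more. It does not call for interactions, raw scaling, or a test read at zero. A reader might infer from the .06 figure that the analysis as written destroys the power of the trial. The text does not support that: the additive form does no harm, and a competent analyst would centre. The loss requires the trigger to be met, a parametric model to be kept although nonparametric tests are expected for suicidality, interactions to be fitted, covariates to be left uncentred, and the zero-covariate line to be reported as primary. All of this stands, so the loss is a risk of an unspecified model and not a feature of the plan.

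A reader might also infer that adjusting for age or BMI can never help. Step 5 shows a modest gain under moderation, so that is too strong.

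Third, one might infer that the triggers let results choose the model and inflate type I error. The spread of age and enrollment BMI is fixed before treatment, the medicines trigger concerns how common use is, and no inflation from the switch has been computed. Nor is it established that the first trigger will always be met. Between-woman spread is very likely at ages 18 to 45, but if the phrase means variation between a woman's two conditions, age would never qualify. What stands is that the choice is open and no later document closes it.

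Finally, the constancy argument does not extend to medicines, and follow-up weight in 7.3.3 leaves BMI not strictly fixed, though the plan does not propose to use weight as a time-varying covariate.

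**Conclusion.** The concern holds as a specification gap with a large possible consequence. An undefined trigger can replace the primary test for all seven outcomes with a model whose terms and test coefficient are not given. Two of its three covariates cannot confound the contrast that they are meant to adjust. Depending on how they enter, power at d = .40 with 30 completers is unchanged, modestly higher, or about .06 instead of about .56. The low figure rests on assumed age and BMI distributions but varies little across those tried, and it applies only to uncentred condition-by-covariate terms. The baseline of .56 depends on the scale of d; at a within-person correlation of .7 the fall is from .78 to .06. The change should be made before analysis.

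**What to change.** Delete the variability trigger in 10.4.2 and the corresponding trigger for medicines in 4.1. In their place:

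- State one primary analysis for every outcome: the within-person difference between condition means, adjusted for condition order (period), with the condition effect and its confidence interval as the primary result.
- Name its nonparametric counterpart in advance, for example a rank-sum comparison of period 1 minus period 2 differences between the two orders, and state when it applies.
- If age or BMI is of interest, mean-centre it, test the condition effect at the covariate means, and report a secondary condition-by-covariate analysis.
- Use within-woman change in medication between the two windows only as a sensitivity analysis, noting that medication use during treatment may itself be affected by condition.
- Bring the sentence on baseline control in 10.4.6 into line.

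The cost is a few sentences, one degree of freedom for condition order (power .563 to .562 at d = .40), and the modest precision gain that centred adjustment could give if age or BMI truly moderates the effect. No visits, data or participants change.
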